4.2.5 Virologic Failures (Only in the Closed Report)

4.3.1 SVR12

4.4.2 HCV Virologic Responses

- The Open Report will be limited to on-treatment HCV RNA. Only the following component will be provided in the Open Report.
 - a) Listing of each participant's HCV RNA results will be provided with calculated visit weeks.

3.2 Final Primary Analysis Report and SVR24 Supplement

The purpose of the final analysis report is to complete the main analyses as described in the protocol, including the analysis of the primary endpoint SVR12.

SAP Version 2.0: The final primary analysis report for the study will occur when SVR12 data are complete. All the components of this plan in Section 4 will be included in the Final Primary Analysis Report, except for SVR24 results which will not yet be available. See Appendix Table B for the timetable. Once the study is complete, SVR24 data table will be generated and distributed to the study team as a supplement to the final primary analysis report.

4 Description of Components

SAP Version 2: Components have been updated.

4.1 Administrative and Baseline Characteristics

4.1.1 Study History

Purpose: To provide a summary of the protocol, any clarification memos and amendments and key events during the study that may be relevant to the study conduct.

- a) A summary of changes to and clarifications of protocol.
- b) A summary of recommendations from SMC reviews.
- c) Description of the accrual process and progress.

4.1.2 Accrual

Purpose: To give a summary of accrual and the distribution of enrollment across sites.

- a) Table of number (%) enrolled by site and month/year
- b) Table of number (%) enrolled by the stratification factor
- c) Number of participants on each regimen with ritonavir-boosted HIV protease inhibitor and tenofovir who participated in the PK sample collection*
- d) Dates of first and last enrollments

* In consideration of the secondary objective on tenofovir PK.

4.1.3 Eligibility Violations and Registration Errors

Purpose: To document any participants who were accrued to the study but were subsequently excluded from analyses due to errors in screening procedures.

- a) Description of each eligibility or screening error and exclusion from analyses.

4.1.4 Baseline Characteristics

Purpose: To describe the study population.

Notes: For all variables, the numbers of participants with available data will be provided. For the lab measures, the values up to and including treatment initiation date will be considered, and the value closest to treatment initiation date will be chosen.

- a) Demographic and health variables: race/ethnicity, sex, age, IVD history, BMI.
- b) Liver-related variables: HCV RNA, APRI, FIB-4, FibroSure, cirrhosis status, method used to determine cirrhosis status, HCV genotype 1 subtype, liver function tests. Listing of HCV resistance mutations detected at study baseline.
- c) HIV-related variables: HIV viral load and CD4 count by ARV receipt.
- d) ARV regimen.
- e) Other: prior HCV treatment (e.g. SOF/PEG, SOF/PEG/RBV, SIM/SOF) and response (relapse, partial response, null response), IL28B.

- ✓ SDAC Validation: All programs generating variables as study-specific will be validated (e.g. APRI, FIB-4).

4.1.5 Study Treatment Status and Duration of Treatment

Purpose: To summarize completeness of study treatment

- a) Study Treatment Status
 - Total number of participants who met the eligibility criteria and initiated study treatment
 - Number of participants who initiated study treatment regimen
 - Number of participants who completed study treatment regimen
 - Summary of reasons for treatment discontinuation, including categories for: completion of prescribed treatment duration, HCV virologic failure (as protocol-defined clinical event), lost to follow-up, adverse events, consent withdrawal, non-adherence, other. For reasons coded as “other”, a listing will be provided.
 - b) Summary statistics (median, Q1, Q3) on time on treatment
- ✓ SDAC validation: All programs generating variables as study-specific will be validated (e.g. treatment regimen, time on treatment).

4.2 Safety

Purpose: To address the safety objectives of the study.

4.2.1 Adverse Events and Protocol-Required Laboratory Tests

- a) Descriptive tables summarizing the adverse events and the number of participants experiencing the events will be provided by grade and by the site report on relationship to study treatment.
- b) Summary table of all diagnoses reported.
- c) Listing of participants with renal toxicity events (defined as Grade ≥ 2 creatinine clearance post-entry or new proteinuria or glucosuria, an increase from entry glucosuria or proteinuria by $\geq 1+$).
 - baseline characteristics: age, sex, race/ethnicity, ART regimen, study treatment, cirrhosis status
 - all available results on: urinalysis protein and protein, creatinine clearance (CrCl), spot protein and creatinine (and protein/creatinine ratio)
 - study treatment modifications
 - study treatment adherence
 - ARV modifications

Notes:

1. The protocol requires grading of events according to The Division of AIDS Table for Grading the Severity of Adult and Pediatric Adverse Events, Version 2.0, November 2014, which is available on the RCC website: <http://rsc.tech-res.com/safetyandpharmacovigilance/gradingtables.aspx>
2. The protocol requires the collection of signs and symptoms, diagnoses, laboratory events that
 - a. are Grade ≥ 3 post-entry
 - b. that led to a change in treatment (excluding indications for RBV dose modification) regardless of grade, or
 - c. that met ICH, EAE or SAE guidelines regardless of grade.

In addition, all creatinine, creatinine clearance (CrCl) and urinalysis results are required. Urine spot protein and creatinine are repeated in participants who develop new proteinuria or glucosuria, an increase from entry glucosuria or proteinuria by $\geq 1+$, or who develop an increase in creatinine of 0.4 from entry or CrCl < 50 , until resolution.

3. Summary tables are based on events reported on the following forms: EVW0314, EVW0315, F2860 (Hematology), F2861 (Chemistry), LBW0144 (Creatinine Clearance) and will not explicitly include events reported on EAEs to DAIDS. Before the database is finalized, the data manager will ensure that all EAE events deemed 'reportable' and included in the SDMC AR001AES table are reflected on the study CRFs.
 4. Events with date of onset or specimen date prior to the first study treatment dose will be excluded.
 5. Deaths will be described separately and not included in the safety summary tables.
- ✓ SDAC validation: All programs generating variables as study-specific will be validated (e.g. variable to indicate participants who experienced a renal toxicity event). User-specific inputs in standard programs will also be validated.

4.2.2 Pregnancy

- a) List and outcome, if any.

4.2.3 Deaths

- a) List and description, if any.

4.2.4 HIV-Related Measures and Changes in ARV Regimen

- a) A summary of CD4 cell count and percent CD4 and changes from baseline at study visits.
- b) A summary of HIV RNA detection status at study visits.
- c) A listing of changes in HIV regimens during the study.

- ✓ SDAC validation: All programs generating variables as study-specific will be validated (e.g. CD4 and HIV RNA categories, changes over time).

4.2.5 Virologic Failures

- a) HIV Virologic Failure

- Details on participants on ART with undetectable HIV RNA at entry who experience HIV-1 virologic failure (as defined in the protocol), including adherence to study regimen and ARV medications, and dose modifications to study medications and ARVs.
- b) HCV Virologic Failures
 - Details on participants who experience HCV virologic failure (as defined in the protocol), including ARV regimen, adherence to study regimen and ARV medications, dose modifications to study medications and ARVs, and the following baseline information: HCV RNA, cirrhosis status, race and ethnicity, HCV genotype, development of resistance-associated variant at the time of virologic failure.
- ✓ SDAC validation: All programs generating variables as study-specific will be validated (e.g. HIV breakthrough, HCV breakthrough).

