NOTE: Acceptable imaging includes a negative ultrasound, computed tomography (CT) scan or magnetic resonance imaging (MRI) within 6 months prior to study entry. Participants who have an ultrasound with results suspicious for HCC followed by a negative CT or MRI of the liver will be eligible for the study.

- 4.1.4 Presence of HIV-1 infection, documented by any licensed rapid HIV test or HIV enzyme or chemiluminescence immunoassay (E/CIA) test kit at any time prior to study entry and confirmed by a licensed Western blot or a second antibody test by a method other than the initial rapid HIV and/or E/CIA, or by HIV-1 antigen, plasma HIV-1 RNA viral load. Two or more HIV-1 RNA viral loads of >1,000 copies/mL, at any time prior to screening, are also acceptable as documentation of HIV infection.
- 4.1.5 Participants must meet one of the following criteria:
  - a) Not currently on ARV with CD4+ T-cell count >500 cells/mm^3 obtained within 42 days prior to study entry at any laboratory that has a CLIA certification or its equivalent.

 b) Not currently on ARV: elite controllers with HIV-1 RNA < 500 copies/mL on all measurements in the 48 weeks prior to study entry and CD4+ T-cell count >200 cells/mm^3 obtained within 42 days prior to study entry at any laboratory that has a CLIA certification or its equivalent. OR c) On a stable, protocol-approved ARV regimen, as noted below, for >8 weeks prior to entry with a CD4+ T-cell count >200 cells/mm^3 obtained within 42 days prior to study entry at any laboratory that has a CLIA certification or its equivalent and a documented plasma HIV-1 RNA level <50 copies/mL by any laboratory, obtained within 42 days prior to study entry, that has a CLIA certification or its equivalent.

NOTE: Approved ARV is limited to efavirenz, rilpivirine, raltegravir, dolutegravir, tenofovir, abacavir, 3TC/FTC, RTV-boosted atazanavir, RTV boosted darunavir (both 800 mg QD and 600 mg BID permitted).

4.1.6 For the first 15 participants taking tenofovir and a PI/r as part of their ARV regimen, willingness and intent to participate in PK component.

NOTE: In the event that 15 participants on PI/r and tenofovir have enrolled into A5348, participation in the PK evaluation will be optional for subsequent participants.

4.1.7 HCV GT-1 within 12 months prior to study entry as determined by the local laboratory.

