### 7.1.6 HIV-1 Virologic Failure

Plasma HIV-1 RNA will be monitored throughout the study for participants on ARV. In this study, HIV-1 viral failure will be defined as confirmed increase in HIV-1 RNA to  $\geq$ 200 copies/mL at any time after study entry, only for participants who are taking ARV.

Since "blips" in HIV-1 RNA may be observed in individuals on ARV in the absence of HIV-1 VF, any increase in plasma HIV-1 RNA ≥200 copies/mL must be confirmed with repeat testing as soon as possible (not to exceed 2 weeks). For participants with confirmed HIV-1 VF, a plasma specimen obtained at the time of confirmation will be sent to the designated central laboratory for evidence of HIV-1 drug resistance. Confirmed HIV-1 VF specimens must have repeated detection of ≥200 copies/mL for HIV-1 drug resistance testing. Results will be reported back to sites in real-time from the designated central laboratory.

Clinical management of HIV-1 VF will be handled by local site investigators according to current HIV treatment guidelines and local standard of care. The A5348 protocol core team must be contacted to notify of any changes in ARV regimen in the event of HIV-1 VF ([contact]).

Investigators should consult section 5.0 and the package insert.

Regarding the potential for a modified ARV regimen for HIV-1 VF: Possible modified ARV regimens should take into account the unique characteristics of the participant and the participant's HIV treatment history as well as known and/or anticipated drug interactions with DAA or DAA+RBV therapy.

If no reasonable salvage HIV regimens compatible with continued HCV DAA or DAA+RBV therapy are deemed available for an individual participant with HIV-1 VF then the participant must discontinue HCV DAA+RBV therapy.

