- 9.2.2.4 HCV RNA <LLOQ (either TD or TND) at post-entry scheduled visits, using the visit windows as defined in section 6.
- 9.2.2.5 HIV-1 RNA > 50 copies/mL at all scheduled visits, using the visit windows as defined in section 6.
- 9.2.2.6 Change in CD4+ cell count from study entry at subsequent scheduled visits, using the visit windows as defined in section 6.
- 9.2.3 Exploratory Outcome Measures
  - 9.2.3.1 HCV resistance mutation at study entry. The set of mutations to be considered will be defined prior to analysis based on the latest information.
  - 9.2.3.2 Development of resistance mutation in SVR12 failures.
  - 9.2.3.3 Tenofovir area under the curve (AUC) at baseline (prior to study treatment initiation) and at week 4.
  - 9.2.3.4 SOF and LDV metabolite concentrations.
- 9.3 Randomization and Stratification

The study is randomized to Arm A and Arm B and stratified by the cirrhosis status. Initially, 15 slots will be reserved for participants taking a PI/r and tenofovir regimen across the two study arms. This will be lifted 3 months after the study is open to accrual, so that the accrual progress is not constrained by the PK objective on tenofovir.

The first 15 participants whose ARV regimen contains HIV PI/r plus tenofovir who enroll to the study must be willing to participate in PK sampling (pre-dose, hour 1 and hour 4) at weeks 0 and 4. After 15 such participants have contributed PK samples, participation in the tenofovir PK sampling is optional. Study accrual may conclude with fewer than 15 participants whose ARV regimen contains HIV PI/r plus tenofovir, since the reservation of 15 slots will be lifted 3 months after the study is open to accrual. There is no minimum or maximum for such participants.

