#### 9.6 Analyses

As a small study to provide supportive data on SVR12, precision is limited, and analyses related to HCV virologic response will be conducted with two-sided 90% CIs. This is noting that the lower limits of these two-sided CIs are equivalent to the limits in the 95% one-sided lower CIs. Analyses related to safety will be conducted with two-sided 95% CIs to be conservative.

The primary objective will be addressed separately in Arms A and B. The proportion of participants within each study arm who achieve SVR12 will be estimated with a two-sided Wilson CI. The analysis will be conducted as modified intent-to-treat (ITT) on participants who meet the eligibility criteria and initiate study treatment. Given the SVR12 definition, a tabulation of reasons for not achieving SVR12 (e.g., detectable HCV RNA, early treatment discontinuation, loss to follow-up) will be an important supplement to the primary analysis on SVR12. The primary analysis timeline will be driven by the last participant's completion of the SVR12 visit, rather than the study completion date. Results from the primary analysis on SVR12 may be presented publicly - for example, at a conference – prior to study database finalization that includes SVR24 completion, when SVR12 data are complete.

The secondary HCV virologic measures will also be analyzed with 90% two-sided Wilson CIs around the observed proportion in each study arm.

The SVR 4, SVR12 and SVR24 differences between the two study arms will be evaluated with 90% two-sided CIs, using the Newcomb score (Wilson) methods.

For the safety analysis, the proportion of participants with events as described in section 9.2.1.2 will be summarized with 95% Wilson CIs around the observed proportions. The worst graded event per participant over time will be used. Descriptive tables summarizing the events and the number of participants experiencing the events will be provided by grade. Descriptive summaries will also be provided on the participants who discontinue the study treatment early, categorized by the reasons for discontinuation. HIV-1 RNA statuses (<50 copies/mL) and CD4+ T-cell count changes from baseline at scheduled visits will be summarized. The summary on HIV-1 and HCV virologic failures will be descriptive, and a listing will be provided with details including time of failure and participant's ARV regimen.

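### SAP 4.2.5(a) puts an entry condition on the HIV-1 virologic failure listing that the protocol does not have, so the listing can omit protocol-defined failures

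*SAP*

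**What the plan says.** **Event definition.** Protocol 7.1.6 defines HIV-1 virologic failure as a confirmed increase to at least 200 copies/mL, "at any time after study entry, only for participants who are taking ARV". Entry HIV RNA plays no part in that definition.

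**Planned protocol reporting.** Protocol 9.6 calls for a descriptive summary of HIV-1 and HCV failures and a listing that includes time of failure and ARV regimen. It sets no entry condition. For HIV RNA by visit, the same section says: "HIV-1 RNA statuses (<50 copies/mL) and CD4+ T-cell count changes from baseline at scheduled visits will be summarized".

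**SAP failure listing.** SAP 4.2.5(a) asks for details on "participants on ART with undetectable HIV RNA at entry who experience HIV-1 virologic failure (as defined in the protocol"). It gives no cut-off for undetectable and no reason for the restriction. The HCV item beside it, 4.2.5(b), has no comparable filter.

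**SAP visit summary.** SAP 4.2.4(b) reads "A summary of HIV RNA detection status at study visits", with no number attached. SAP 4.4.4 restates Secondary Objective 9 with the threshold of 50 copies/mL and refers it to 4.2.4.

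**Eligibility on ARV.** Protocol 4.1.5(c) requires "a documented plasma HIV-1 RNA level <50 copies/mL by any laboratory, obtained within 42 days prior to study entry".

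**The concern.** The SAP says that it uses the protocol's definition, yet it lists only a subset of the people to whom that definition applies. The subset is chosen on baseline HIV control: those whose control was least secure at entry are removed before failures are listed. Secondary Objective 9 (protocol 1.3.9) asks how LDV/SOF-based retreatment influences HIV parameters, so these are people whose later course a reader would want to see.

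The stakes are in the completeness of a safety listing. After early closure, SAP 2.5.2 says that the report will be descriptive and made up mostly of listings. With so few participants, one missing line could change what the report says about HIV control.

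**Working it through.** No sample size, power or interval is involved, so the check compares the texts and works through the possible cases.

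**Step 1. Can entry HIV RNA differ from the qualifying value?** Yes.
- The qualifying value may be up to 42 days old (protocol 4.1.5(c)).
- The Schedule of Events (protocol 6.1) has a separate HIV-1 RNA sample at entry for participants taking ARV.
- SAP 2.8 takes the entry value from the day of treatment dispensation, or the closest evaluation before it. Where the entry sample exists, it therefore replaces the screening result.

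**Step 2. Who is counted if an increase to at least 200 copies/mL is confirmed on ARV after entry?**

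| Entry HIV RNA | Protocol 7.1.6 and 9.6 | SAP 4.2.5(a) |
|---|---|---|
| Not detected | Counted | Counted |
| Detected, below 50 | Counted | Depends on what undetectable means |
| 50 to 199 | Counted | Omitted |
| 200 or more | Counted if the later value is a confirmed increase | Omitted |

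The third row settles the point. For example, a participant qualifies below 50, is at 80 at entry, and has 400 confirmed around week 4. The protocol counts this as a failure and sends a sample for resistance testing. The SAP listing has no line for it. The second row turns on an unstated cut-off: if undetectable means below 50, that gap closes and the third row remains.

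**Step 3. Direction.** The SAP condition only removes people and adds none. Against the protocol's count, the error is zero or an undercount.

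**Step 4. Does another output recover the omitted case?** Not as a failure.
- SAP 4.2.4(b) is a by-visit summary. It does not identify a confirmed rise to 200 or more, or link it to adherence and dose changes.
- SAP 4.2.4(c) lists ARV changes, which a failure may or may not prompt.
- SAP 4.1.4 gives baseline viral load only.

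**Step 5. Size.** The documents do not say how many of the 7 had a detectable entry value, so the possible range is 0 to 7. One participant is 1/7 = 14% of those enrolled. As an illustration only, assume that all 7 were on ARV and that 5% to 15% were detectable at entry. Then 7 × 0.05 = 0.35 to 7 × 0.15 = 1.05 people would fall outside the listing, and a failure is lost only if one of them also fails.

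**Step 6. The 50 copies/mL threshold.** Objective 9 and protocol 9.6 use below 50. Protocol 9.2.2.5 uses "HIV-1 RNA > 50 copies/mL at all scheduled visits". A value of exactly 50 is neither below 50 nor above it. SAP 4.2.4(b) states no cut-off.

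**Step 7. Content of the listing.** Protocol 9.6 asks for time of failure and ARV regimen. SAP 4.2.5(a) names adherence and dose modifications but neither of those two items.

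**The case against.** The best defence is that Objective 9 speaks of maintaining HIV RNA below 50, and only someone suppressed at the start can maintain suppression. Viremia already present before the first LDV/SOF dose says little about an effect of that drug. On this view the filter is a choice of analysis population. The argument is reasonable, but the SAP does not make it, and it does not discharge the separate commitment in protocol 9.6 to list HIV-1 failures. An entry-value column lets the reader make the same distinction without losing the case.

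It is also fair to say that failures are confirmed, tested for resistance and managed in real time under protocol 7.1.6 whatever the SAP lists. That stands: the defect is in reporting.

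A reader might infer more than the documents support:

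- *That the SAP redefines HIV-1 failure.* It keeps the protocol's event and narrows whose details are given.
- *That the outcome of HIV RNA below 50 has been dropped.* SAP 4.4.4 names it and refers it to 4.2.4, whose validation note mentions HIV RNA categories. What is missing is a written cut-off. Nothing shows that detection status means the assay's target-detected result, so it cannot be said that values below 50 will be read as loss of control.
- *That failures after starting ARV on study are a clear second gap.* The protocol requires an increase to at least 200. Someone already viremic off ARV would need a further rise, and HIV RNA after screening is not required off ARV. This case is strained.
- *That interim oversight was compromised.* Component 4.2.5 is in the closed SMC report, but SAP 3.1 records one review, with an abbreviated report on 7 participants after accrual had closed.
- *That a set percentage of an arm is lost.* The split by arm is not documented, and no HIV failure proportion is planned for estimation.

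**Conclusion.** The mismatch holds as a matter of text. SAP 4.2.5(a) adds an entry condition found in neither protocol 7.1.6 nor protocol 9.6, and following it can omit a protocol-defined failure. The clear case is a participant on ARV who qualified below 50, was at 50 to 199 at entry, and then had a confirmed increase to at least 200. This conclusion does not depend on how undetectable is read, because no sensible reading includes values of 50 or more when the trial's suppression threshold is below 50.

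The practical effect is likely to be small and may be nil: 7 participants, all those on ARV suppressed within 42 days before entry, and a descriptive report. The correction is still worth making because the error can run only one way and the report consists mainly of listings. The missing cut-off in SAP 4.2.4(b) and the wording of protocol 9.2.2.5 are minor alignments, the latter affecting only a value of exactly 50.

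**What to change.** 1. In SAP 4.2.5(a), delete the condition on undetectable HIV RNA at entry. List every participant who meets protocol 7.1.6 while on ARV.
2. Show entry HIV RNA as a column of that listing, and add time of failure and ARV regimen as protocol 9.6 asks.
3. In SAP 4.2.4(b), state the categories as HIV-1 RNA below 50 versus 50 copies/mL or more, among those on ARV.
4. Align protocol 9.2.2.5 with the objective, so that its complement of below 50 is 50 or more.

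The cost is a few lines of SAP wording, one programming condition, some added listing columns and a small protocol clarification. The visit and ARV data are already collected. The one downside is that a failure in someone already viremic at entry will appear in the listing. The entry-value column makes that plain.
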